4.4.2 Primary Efficacy Endpoint

The primary endpoint is annualized rate of decrease in percentage of predicted FVC through Week 52, which will be compared across treatment arms with use of a random slope model on observed cases at a 0.05 two-sided significance level.

The statistical model is as follows:

$$FVC_{ijk} = (\beta_0 + \beta_{0k}) + (\alpha_i * \beta_1 + \beta_{1k}) * t_k + \eta_k + \epsilon_{ijk}$$

where FVC_{ijk} is the predicted FVC for kth patient at visit j in treatment group i; β_0 is the intercept; α_i and β_1 is the interaction term of the treatment effect ($i = \text{lebri or placebo}$) and the slope; t_k is assessment time (continuous in year) for patient k; η_k is the effect of baseline lung function (defined as $FVC < 50\%$ vs. 50% to 75% vs. $> 75\%$ predicted) for the kth patient; β_{0k} and β_{1k} are the random components for intercept and slope; ϵ_{ijk} is the random error for kth patient at time j; β_{0k} , β_{1k} , and ϵ_{ijk} are assumed to be independent and normally distributed with mean 0 and variance of σ_0^2 , σ_1^2 , and σ_ϵ^2 respectively.

Of note, because of a relatively large number of strata defined by the randomization stratification factors, the analysis will be adjusted for baseline lung function only because baseline FVC may impact the clinical disease course.

From the model, least squares means for the annualized rate of decrease in each treatment arm and the difference between the two treatment arms will be provided with

95% CIs. The model implicitly imputes missing data based on an individual's estimated rate of worsening of lung function prior to study visit discontinuation (i.e., assuming missing at random).

There are several different approaches to summarizing the treatment effect which are ways of understanding the results rather than independent endpoints. For summarizing treatment effect the following will be provided but not considered as separate endpoints or hypotheses.

- Change from baseline to landmark visit time expressed as absolute and relative difference
- Difference in annual rate of decrease expressed as absolute and relative difference
- Categorical absolute change from baseline to each visit time with categories of decrease of $\geq 10\%$ or death before the visit, decrease of 10% to $>0\%$, stability or improvement of change $\geq 0\%$

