Change from baseline in percentage of predicted FVC at Week 52 will be analyzed as a sensitivity analysis with use of a mixed-effects model for repeated measures (MMRM) on observed cases at a 0.05 two-sided significance level.

The statistical model is as follows:

$$\text{Chg}_{ijk} = \beta_0 + \alpha_i * \beta_j + \eta_k + \varepsilon_{ijk}$$

where Chg_{ijk} is the change in percentage of predicted FVC for k th patient at visit j in treatment group i ; β_0 is the intercept; $\alpha_i * \beta_j$ is the interaction term of the treatment and categorical visit effect ($i = \text{lebri or placebo}$, $j = \text{Weeks 1, 4, 12, 24, 36, 44, and 52}$; $\alpha_{\text{placebo}} * \beta_{12} = 0$); η_k is the effect of baseline lung function (defined as $\text{FVC} < 50\%$ vs. 50% to 75% vs. $> 75\%$ predicted) for the k th patient; ε_{ijk} is the random error for k th patient at time j and is assumed to be independent and normally distributed with mean 0 and unstructured variance-covariance V . If this analysis fails to converge, analyses using compound symmetry or first order autoregressive structures as alternatives will be investigated.

From the model, least squares means for the absolute change from baseline as well as placebo corrected absolute changes with 95% CIs for each treatment arm at each post-baseline visit will be estimated.

Other sensitivity analyses using various imputation/analysis strategies will also be performed. See Section 4.4.5 for details.

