4.4.4 Exploratory Efficacy Endpoints

Time-to-Event Endpoints

These endpoints will be analyzed and summarized with use of the same methods for the time-to-event secondary endpoints.

Change-from-Baseline Endpoints

These endpoints will be analyzed and summarized with use of the same methods as the endpoint—change from baseline in percentage of predicted FVC in Section 4.4.2.

Annualized Rate of Decrease Endpoints

The annualized rate of decrease in SpO₂ (%) over 52 weeks will be analyzed and summarized with use of the same method as for the annualized rate of decrease in percentage of predicted FVC.

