4.4.6 Subgroup Analyses

Subgroup analyses will be performed to assess the impact of select baseline characteristics (see [Table 1](#)) on the change from baseline in percentage of FVC at 52 weeks, by examining the interaction with the study drug with use of the MMRM model. Each baseline factor will be analyzed separately. Some categories may be grouped to allow sufficient sample size for interpretation.

Table 1 Subpopulation Definitions

Baseline Characteristics	Categories
Geographic region	U.S. ROW
Age at randomization	< 65 years ≥ 65 to < 75 years ≥ 75 years
Sex	Female Male
Race/ethnicity	White Nonwhite
Time from IPF diagnosis to randomization	< 1 year ≥ 1 year
Baseline %FVC	< 55% predicted 55% to < 75% predicted ≥ 75% predicted
FEV ₁ /FVC	< 0.80 ≥ 0.80
Hgb-corrected DL _{CO} (% predicted) ^a	< 35% 35% to < 50% ≥ 50%
GAP Index (see Appendix 6)	I/II or III
Extent of fibrosis on HRCT at baseline, expressed as a QLF score	Divided at the median for initial summary score
Periostin	< 50 ng/mL ≥ 50 ng/mL
Duration of prior pirfenidone exposure (for Cohort B only)	0 (started after informed consent) < 1 year ≥ 1 year

FEV₁=forced expiratory volume in 1 second; FVC=forced vital capacity;
HRCT=high-resolution computed tomography; QLF=quantitative lung fibrosis; ROW=rest of world.

Note: Hispanic/Latino ethnicity grouped with nonwhite for subgroup analyses.

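### The MMRM's convergence fallback assumes one variance at all visits, so if it is used with model-based errors the Week 52 standard error for percent predicted FVC is too small

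*Combined protocol and SAP*

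**What the plan says.** The primary analysis in SAP 4.4.2 compares annualized rates of decrease "with use of a random slope model on observed cases at a 0.05 two-sided significance level". In that model two patient-level terms "are the random components for intercept and slope", each with its own variance.

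The same section then gives a second model: "Change from baseline in percentage of predicted FVC at Week 52 will be analyzed as a sensitivity analysis". It is an MMRM with visit as a category ("Weeks 1, 4, 12, 24, 36, 44, and 52") and errors that are "normally distributed with mean 0 and unstructured variance-covariance V". For non-convergence the section says: "If this analysis fails to converge, analyses using compound symmetry or first order autoregressive structures as alternatives will be investigated". It names no heterogeneous-variance version, no order of preference between the two structures and no robust standard error.

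Three other parts of the SAP reuse this MMRM:

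- Sensitivity analysis D (SAP 4.4.5) applies it with deaths imputed at the worst observed value.
- The subgroup analyses (SAP 4.4.6) assess each baseline factor "by examining the interaction with the study drug with use of the MMRM model".
- For the exploratory change-from-baseline endpoints, SAP 4.4.4 says: "These endpoints will be analyzed and summarized with use of the same methods as the endpoint", and names change from baseline in percent predicted FVC as that endpoint.

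**The concern.** Compound symmetry and first order autoregressive, without the word heterogeneous, both give the change at Week 1 the same variance as the change at Week 52. AR(1) also treats visit gaps of 3, 8, 12, 12, 8 and 8 weeks as equal. The random slope model in the same section implies something different: patients diverge over time, so change varies least at Week 1 and most at Week 52.

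The contrast of interest is at Week 52. A variance pooled over early, low-variance visits gives that contrast an interval that is too narrow. A sensitivity analysis is meant to test the primary result, and one with understated errors can give false reassurance or make a null subgroup interaction look real. With two candidates and no rule for choosing, the choice could also be made after both results have been seen.

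**Working it through.** **Inputs from the documents.** SAP 2.3: Week 52 change SD 7; 75 per arm with a difference of 3.6 (Cohort A); 165 per arm with a difference of 2.4 (Cohort B); two-sided 0.05. SAP 4.4.2: the seven visits, and a random intercept, random slope and independent error.

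**Assumed.** The measurement SD, σₑ. The documents give no measurement SD, no SD at earlier visits and no within-patient correlation, so a range is shown. The main table takes data as complete, and the baseline lung function category is ignored.

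**The plan's own figure.** The SE of the Week 52 difference is 7·√(2/n): 7·√(2/75) = 1.143 and 7·√(2/165) = 0.771. Power is Φ(3.6/1.143 − 1.96) = 88.3% and Φ(2.4/0.771 − 1.96) = 87.6% (87.9% and 87.4% with the noncentral t). SAP 2.3 says over 85%, which agrees. The documents state no Week 52 SE; 1.143 and 0.771 are what SD 7 implies when the Week 52 variance is left free.

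**Variance implied by the random slope model.** The intercept cancels in a change from baseline, so with t in units of 52 weeks

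Var(change at t) = σ₁²·t² + 2σₑ².

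At t = 1 this equals 49, so σ₁² = 49 − 2σₑ². For σₑ = 3, the visit SDs run 4.24, 4.26, 4.43, 4.96, 5.73, 6.34 and 7.00.

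**Compound symmetry.** With complete data the fitted common variance is the average over visits.

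- Mean t² = (1 + 16 + 144 + 576 + 1296 + 1936 + 2704)/(7 × 2704) = 6673/18928 = 0.3525.
- With p = 2σₑ²/49 as the noise share, SE ratio = √[0.3525·(1 − p) + p].
- Example, σₑ = 3: p = 18/49 = 0.367, and √(0.223 + 0.367) = 0.77.

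**AR(1).** The variance and correlation were found numerically by minimising the expected Gaussian likelihood against the implied covariance matrix.

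**Type I error.** Real two-sided α = 2·[1 − Φ(1.96 × ratio)].

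| σₑ (assumed) | Noise share p | CS ratio | CS real α | AR(1) ratio | AR(1) real α | CS SE, 75 per arm (correct: 1.143) |
|---|---|---|---|---|---|---|
| 1.5 | 9% | 0.64 | 0.21 | 0.69 | 0.18 | 0.734 |
| 2 | 16% | 0.68 | 0.18 | 0.71 | 0.17 | 0.774 |
| 3 | 37% | 0.77 | 0.13 | 0.78 | 0.13 | 0.878 |
| 3.5 | 50% | 0.82 | 0.11 | 0.83 | 0.10 | 0.940 |
| 4.3 | 75% | 0.92 | 0.07 | 0.92 | 0.07 | 1.048 |
| 4.95 (no slope variance) | 100% | 1.00 | 0.05 | 1.00 | 0.05 | 1.143 |

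The ratios do not depend on n, so they hold for 165 per arm, and they are the same at SD 8 for a given noise share. Simulation of compound symmetry with 75 or 165 per arm gave a type I error of 18.5% to 18.7% at σₑ = 2 and 13.2% to 13.5% at σₑ = 3, against 4.7% to 5.3% for unstructured. AR(1) was not simulated. With an assumed 20% uniform dropout the compound symmetry ratios fall slightly, to 0.61, 0.69, 0.81 and 0.91 at noise shares of 10%, 25%, 50% and 75%.

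With complete data the Week 52 point estimate is the same under every structure; only its SE changes. The ratio applies equally to a Week 52 subgroup interaction contrast, whose SE scales with the same fitted variance.

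**The case against.** **The fallback may never be used.** The planned structure is unstructured. Seven visits give 7 × 8/2 = 28 covariance parameters for about 150 and 330 patients, which is not an extreme load, and nothing in the documents points to non-convergence. This stands, and it limits the weight of the point.

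**The text says only that alternatives will be investigated.** It does not bind the sponsor to report them or exclude others. That is fair, but these are the only two structures named and no selection rule is given. Leaving the choice open does not make it safer.

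**No trial claim depends on this model.** A reader might infer that the 7% to 21% applies to the trial's confirmatory error. It does not. The primary test is the random slope model, and none of the tests in the fixed sequence of SAP 4.4.1 uses the MMRM. Sensitivity analyses A, B and C do not use it either, and A addresses Week 52 change without a repeated-measures covariance.

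**A reader might infer that the Week 52 SE would be far too small.** The documents cannot show this. The size depends on the split between slope variance and measurement noise, which they do not give, and it shrinks to nothing as slope variance does.

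**A reader might carry the figures to everything that reuses the MMRM.** They do not transfer. By the schedules of assessments, ATAQ-IPF and SGRQ have five scheduled post-baseline visits, Borg CR10 has two (three covariance parameters, so non-convergence is very unlikely) and quantitative HRCT has one. SAP 2.2.3 sends HRCT and biomarkers to a separate plan. Analysis D's death imputation does not follow the variance formula used here.

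**Conclusion.** The defect is real and its direction needs no outside figure: whenever there is slope variance, a homogeneous-variance fallback with model-based errors understates the Week 52 SE for percent predicted FVC. At Week 52 SD 7 and an assumed measurement SD of 1.5 to 4.3 points, the understatement is about 8% to 36% and the real two-sided α about 7% to 21%. Confidence is high on direction and moderate on size.

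The figures apply to the Week 52 MMRM sensitivity analysis and the FVC subgroup interaction tests. Analysis D and any exploratory change endpoint measured at repeated visits share the direction, but no size was computed for them. It matters only if the unstructured fit fails. It is still worth correcting, because a fallback has to be valid in the one situation where it is used.

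**What to change.** Replace the fallback sentence in SAP 4.4.2 with an ordered list, using the first structure that converges:

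1. heterogeneous Toeplitz (7 variances and 6 correlations, 13 parameters);
2. heterogeneous AR(1);
3. heterogeneous compound symmetry.

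State that the empirical (sandwich) standard error is used for any structure other than unstructured, and that the rule applies wherever the MMRM is reused (SAP 4.4.4, 4.4.5 D and 4.4.6).

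The cost is one sentence and a covariance option in the program. SAP section 1 says the plan is being amended before Cohort B is unblinded, so the change fits there. When the fallback is used, the Week 52 interval will be wider than under the current fallback: 1/0.92 to 1/0.64 before rounding, or about 9% to 56% over the assumed range. That is the correct width. A heterogeneous structure may itself fail to converge, which is why the list is ordered.

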4.4.3 Secondary Efficacy Endpoints

Time-to-Event Endpoints

The log rank test stratified by baseline lung function ($\text{FVC} < 50\%$ vs. 50% to 75% vs. $> 75\%$ predicted) will be used to compare the time to event endpoints between two treatment arms. The hazard ratio and its 95% CI will be estimated using a Cox regression model

stratified by baseline lung function. In fitting the Cox model, ties will be handled with the approximate likelihood method of Efron (1977). Kaplan-Meier plots will be provided.

Time-to-event will be measured in reference to the date of randomization. The primary efficacy assessments for the randomized placebo-controlled period are made on through the Week 52 visit, assessment on this day will be included for analyses of the randomized placebo-controlled period, but subsequent assessment during the open-label period or after Week 52 will be excluded. Patients are considered to be in the placebo controlled period even if they have discontinued study treatment if they would still be receiving placebo controlled study treatment had they not discontinued. For time to non-elective hospitalization or death from any cause, time to first event of acute IPF exacerbation, time from randomization to death from any cause, and time to respiratory hospitalization, patients not experiencing an event will be censored at the earlier of last known alive day, study day 368 or the last date during the placebo-controlled period.

For time to first occurrence of a $\geq 10\%$ absolute decrease in percentage of predicted FVC or death from any cause, time to PFS, time to first occurrence of a $\geq 15\%$ decrease in percentage of predicted DL_{CO} or death from any cause, and time to first SGRQ Total Score ≥ 7 or death from any cause, deaths which occur within 168 days after the last clinic assessment and before the week 52 visit (and before start of open label treatment) will be counted as events. For the PFS analysis, hospitalization will be counted as events following the same rule as for death. Patients without an event will be censored at the last clinic assessment during the placebo controlled period. Any patients who undergo lung transplantation will be censored at the date of the transplant. Sensitivity analyses will be provided with lung transplant counted as an event for PFS and time from randomization to death or non-elective hospitalization from any cause. For the sensitivity analyses, only lung transplant, death, or non-elective hospitalization which occur within 168 days after the last clinic assessment and before the week 52 visit (and before start of open label treatment) will be counted as events.

Annualized Rate of Decrease Endpoints

The annualized rate of decrease in FVC (mL/year) will be analyzed and summarized with use of the same method as for the annualized rate of decrease in percentage of predicted FVC. Diffusing capacity, 6MWT distance, and the ATAQ-IPF score will also be analyzed and summarized with the same methods. For the annualized rate of decrease in FVC (mL/year) height, sex, and age will be included in the model as covariates.

Categorical summaries will be provided with categories of decrease of ≥ 50 meters or death before the visit, decrease of 50 to >0 meters, and stability or improvement of ≥ 0 meters for the 6MWT distance; summaries will be provided with categories of decrease of $> 15\%$ or death before visit, decrease of 15% to $>0\%$, stability or improvement of $\geq 0\%$ for percentage of predicted DL_{CO}.

Rules for missing ATAQ-IPF V3 and SGRQ data are described in Section 4.8.

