4.5.11 Non-Elective Hospitalizations

At each study visit, the investigator will ask directed questions to assess the possibility that the patient experienced a non-elective hospitalization(s) per protocol over the preceding 4 weeks. Given that non-elective hospitalizations are a component of the primary endpoint in this study, a dedicated eCRF will be used to record information regarding a protocol-defined hospitalization event. A hospitalization must also be reported as a serious adverse event as per Section 5.2.2.

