For time to event endpoints, the log rank test stratified by baseline lung function (FVC <50% vs. 50% to 75% vs. >75% predicted) will be used to compare the time to event endpoints between the two treatment arms. Time will be measured relative to the date of randomization (Day 1). Patients who do not experience the event will have their data censored on the last date during the placebo-controlled period when, on the basis of the assessments in accordance with this protocol, the patient can be considered to have been event-free. Any patients who undergo lung transplantation will be censored at the date of the transplant. Sensitivity analyses will be provided with lung transplant counted as an event for PFS and time from randomization to death or non-elective hospitalization from any cause.

The primary efficacy assessments for the randomized placebo-controlled period are made on the study day of initiation of the open-label lebrikizumab through Week 52. Assessment on this day will be included for analyses of the randomized placebo-controlled period, but subsequent assessment during the open-label period or after Week 52 will be excluded.

The hazard ratio and its 95% CI will be estimated with the use of a Cox regression model stratified by baseline lung function. In fitting the Cox model, ties will be handled with the approximate likelihood method of Efron (1977). Kaplan-Meier curves will be provided.

Summary statistics of the *ATAQ-IPR* and *SGRQ* endpoints and the changes from baseline will be calculated at each assessment time-point for each treatment group. The mean, standard error, and median of the absolute scores and the mean changes from baseline (and 95% CIs) between treatment groups will be reported for the endpoint. For scores involving change from baseline, patients without baseline values will be excluded from the analyses. Line charts depicting the means and mean changes of subscales over time will be also provided. Scoring for the questionnaire will be based on relevant user manuals.

Frequencies and percentages of missing data for the *ATAQ-IPR* and *SGRQ* endpoints will be compared between the two treatment arms.

Additional details for summarization, sensitivity analyses, and type I error control are provided in the SAP.

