Appendix 4 Schedule of Assessments: Safety Follow-Up Period

WEEK post last dose	4 ^a	12	18 (final visit)
Day post last dose (assessment window)	28 (± 3)	84 (± 3)	126 (± 3)
Visit	SFU1	SFU2	SFU3
Limited physical exam ^b	x		x
Weight	x		x
Vital signs ^c	x	x	x
Resting pulse oximetry	x	x	x
Single ECG (all patients) ^d	x		x
Spirometry ⁱ	x	x	x
DLco	x	x	x
6MWT/BorgCR10 ^e	x		
ATAQ-IPF ^f	x		x
SGRQ ^f	x		x
EQ-5D ^f	x		x
Hematology ^g	x	x	x
Chemistry ^h	x	x	x
Urinalysis ⁱ	x		
Urine pregnancy test ^j	x		
Serum PK sample ^k	x	x	x
Plasma PD sample ^{k,l}	x	x	x
Serum PD sample ^{k,l}	x	x	x
Serum antibodies ^k	x		x

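### SAP 4.4.3 censors the hospitalization and exacerbation endpoints at the last day known alive, not the last day those events were assessed, so an arm with more unassessed time could look better

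*Combined protocol and SAP*

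**What the plan says.** SAP 4.4.3 names four endpoints: non-elective hospitalization or death, and then "time to first event of acute IPF exacerbation, time from randomization to death from any cause, and time to respiratory hospitalization". For all four, "patients not experiencing an event will be censored at the earlier of last known alive day, study day 368 or the last date" of the placebo-controlled period. The third limit does not shorten follow-up for someone who stops drug, because "Patients are considered to be in the placebo controlled period even if they have discontinued study treatment", provided they would otherwise still be on blinded treatment. The SAP does not define the sources for last known alive.

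Two other rules in the documents differ:

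- Protocol 6.4.2 stops follow-up at the latest day in that period for which, judged from protocol assessments, "the patient can be considered to have been event-free". SAP section 1 says the SAP supersedes the protocol on analysis.
- For PFS and the FVC, DLco and SGRQ time-to-event endpoints, SAP 4.4.3 says: "Patients without an event will be censored at the last clinic assessment during the placebo controlled period". Deaths up to 168 days after that assessment, and before Week 52, still count. For PFS, hospitalizations count in the same way.

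Protocol 4.5.11 has the investigator ask at each visit whether "the patient experienced a non-elective hospitalization(s) per protocol over the preceding 4 weeks"; 4.5.12 does the same for exacerbation. Both event types are also reported as adverse or serious adverse events.

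**The concern.** A censoring date should be the last day on which the event would have been recorded had it occurred. For death, that is the last day known alive. For hospitalization and exacerbation, it is the last contact at which someone looked for them. Any time between the two enters the risk set although no event can be seen in it. That lowers the estimated rate and raises the Kaplan-Meier curve, and if one arm has more such time, it moves the hazard ratio in that arm's favour.

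The stake is the fixed sequence in SAP 4.4.1, where respiratory hospitalization is the third key secondary endpoint and exacerbation or death the fourth.

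**Working it through.** **Plan's own figures.** The documents give no event rate, hazard ratio, withdrawal rate or power for these endpoints, so there is no stated figure to reproduce on this point. The stated power is for the primary endpoint. For Cohort B (165 per arm, difference 2.5, SD 8), z = 2.5 / (8 × √(2/165)) = 2.84, and power = Φ(2.84 − 1.96) ≈ 81%, against a stated 80%. It reproduces and is unaffected.

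**Can a gap arise under the text?** Under protocol 4.6.1.1, a patient who stops drug and cannot continue assessments should at least enter safety follow-up, which ends 18 weeks after the last dose. With a last dose at Week 20, scheduled contact ends at Week 38, which is 52 − 38 = 14 weeks before Week 52. Under protocol 5.6, serious events after the reporting period need be notified only if believed drug-related. If the site happens to know the patient is alive at Day 368, the SAP rule credits those 14 weeks as event-free. Whether sites obtain such information is not stated.

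**Closed form, upper-end case.** Assumptions: hazard λ = 0.25 per year in both arms; a fraction p leaves, uniformly over the year; every leaver is known alive to one year; no events are recorded after leaving.

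- Stayer: events 1 − e^(−0.25) = 0.2212; person-years 0.2212 / 0.25 = 0.8848.
- Leaver: events 1 − 0.8848 = 0.1152; assessed person-years 0.1152 / 0.25 = 0.4608.
- Credited but unassessed time per leaver: ∫₀¹ (1 − u) e^(−0.25u) du = 0.8848 − 0.4240 = 0.4608. The leaver's person-years under the SAP rule are therefore 0.9216.
- Apparent rate = [(1 − p) × 0.2212 + p × 0.1152] / [(1 − p) × 0.8848 + p × 0.9216].

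| p | Events | Person-years | Apparent rate | Understated by |
|---|---|---|---|---|
| 5% | 0.2159 | 0.8866 | 0.2435 | 2.6% |
| 10% | 0.2106 | 0.8885 | 0.2370 | 5.2% |
| 20% | 0.2000 | 0.8922 | 0.2242 | 10.3% |

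With a true ratio of 1.00, 20% versus 10% leaving gives 0.2242 / 0.2370 = 0.946, and 20% versus 5% gives 0.2242 / 0.2435 = 0.921.

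**Simulation with shorter gaps.** Log-rank test, 165 per arm, 4,000 trials per scenario, true hazard ratio 1, 20% annual event risk, leaving times uniform over 368 days. The gap is the time from last event assessment to last known alive, capped at Day 368. Cells show the apparent hazard ratio for the arm with more loss (for equal loss, one arm against the other), then its false wins (nominal 2.5%).

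| Gap | 20% vs 10% leave | 30% vs 10% leave | 15% vs 15% leave |
|---|---|---|---|
| None | 1.00; 2.3% | 1.00; 2.5% | 1.00; 2.5% |
| 28 days | 0.99; 2.8% | 0.98; 3.2% | 1.01; 1.8% |
| 126 days | 0.96; 3.5% | 0.93; 5.2% | 1.00; 2.2% |
| To Day 368 | 0.94; 4.3% | 0.89; 7.0% | 1.00; 2.4% |

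At 10% annual event risk the worst hazard ratio is again 0.89, with false wins of 5.2%. Censoring at the last event assessment gives hazard ratios of 0.99 to 1.01 and two-sided type I error of 4.3% to 5.7% in every scenario, which is simulation noise around 5%.

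These calculations treat the endpoint as a single non-fatal event. In the composite with death, only the hospitalization part is affected.

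**The case against.** The best reply is that the gap may be small or absent. Hospitalizations and exacerbations are also adverse-event reports; protocol 5.3.1 has investigators seek adverse events at every contact, so a contact that shows a patient alive is normally one where these events are sought too. Patients who only stop drug are encouraged to complete all assessments. Nobody is followed after withdrawing consent (protocol 4.6.1.2), and the documents describe no vital-status sweep. The sentence extending the placebo-controlled period can also be read with SAP 4.4 as meaning patients who stopped drug but stayed in the study. All of this stands as a limit on size. It does not make last known alive the right date for these events, and the rule offers no protection where the two dates differ.

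The PFS comparison is also imperfect. Counting hospitalizations up to 168 days after the last clinic visit shows that the SAP expects some data beyond visits. But that allowance has a time limit, and the present rule has none of its own.

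The confirmatory stake is conditional as well: respiratory hospitalization is formally tested only if the primary endpoint, all-cause death and DLco all succeed, and non-elective hospitalization or death is not in the sequence.

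A reader might also infer that the 4-week questions leave safety follow-up unobserved. Follow-up visits fall 28, 84 and 126 days after the last dose, so (84 − 28 − 28) + (126 − 84 − 28) = 42 of 98 days lie outside those questions. The documents do not support that reading, because the general adverse-event question in protocol 5.3.2 covers the whole interval since the last visit.

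**Conclusion.** The censoring rule is wrong in principle for three of its four endpoints, and it departs from the protocol's rule. It is a stated rule that can credit unassessed time as event-free, so more than a definition is needed. A reader might infer that the arm with more withdrawals will necessarily look better. The documents do not support that: bias needs vital status to outlast event assessment, and more so in one arm, and neither is quantified.

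Under the stated assumptions, the ratio falls from 1.00 to about 0.98 to 0.99 for a 28-day gap, and to about 0.946 (20% versus 10% leaving) or 0.92 (20% versus 5%) if every leaver is known alive to one year. The most extreme case run, 30% versus 10%, gives about 0.89. With no gap or equal loss the bias is nil. The correction is still worth making before Cohort B is unblinded, because it is cheap and changes nothing if the gap is zero.

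**What to change.** In SAP 4.4.3:

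1. Keep last known alive for time to death only, and list its sources.
2. For respiratory hospitalization, acute exacerbation, and non-elective hospitalization or death, censor event-free patients at the last visit or contact at which hospitalizations and exacerbations were assessed, including through adverse-event reports. Cap this at Day 368 and the end of the placebo-controlled period.
3. For endpoints that include death, count deaths after that contact by the existing 168-day rule. Some such limit is needed: counting late deaths while survivors stop contributing earlier biases in the opposite direction. The 168-day limit bounds this bias but does not remove it.
4. Report the present last-known-alive rule as a sensitivity analysis.
5. Reconcile the exacerbation endpoint, which includes death in SAP 4.4.1 but not in 2.2.2 or 4.4.3.

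Leave the 4-week wording in protocol 4.5.11 and 4.5.12 alone. Enrolment is complete, and an amendment could not recover answers already given.

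The cost is a few sentences in the SAP, one added sensitivity analysis and slightly less follow-up time for early leavers. Cohort A is already unblinded, so there the revised rule can only be a supportive re-analysis.
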